adherence indicators and the surveillance arm will be obtained. To examine whether among all participants with a lung nodule ≤ 15 mm, more intensive surveillance will be associated with worse adherence to the surveillance protocol than less intensive surveillance, we will use hierarchical logistic regression that includes random site effects, with and without adjusting for potential confounders including age, gender, ethnicity/race, smoking, BMI, nodule size, and any facility-level factors balanced during the randomization.

Sample size and power calculations by aim

Preliminary data from a retrospective study of patients who underwent one or more chest CT scans at KPSC (2006-2012) showed that 76% of chest CT scans are performed in unique patients, and that approximately 30% of these individuals will have a prior history of cancer. Of the remainder, approximately 32% of unique patients (with no prior cancer diagnosis) who undergo chest CT will have a pulmonary nodule ≤ 30 mm, and 72% of all nodules measure ≤ 15 mm. Thus, we expect that approximately 16% of all unique patients who undergo chest CT will have a qualifying pulmonary nodule measuring ≤ 15 mm and no prior history of cancer. Data provided by participating sites indicates that more than 376,000 chest CT scans will be performed during the planned 20-month enrollment period in over 279,500 unique individuals (**Table 1**). This translates to an estimated target population size of approximately 45,000 patients with qualifying nodules. Allowing for site-level variation in the proportion of patients with a prior history of cancer and patients with nodules detected on prior chest CT scans, we will passively enroll a minimum of 35,200 individuals with a nodule ≤ 15 mm at one of the 14 health systems (24 individual study sites for cluster randomization) during the initial 28-month recruitment period. To allow time to complete the evaluation and accrue outcomes, patients will be followed for at least 2 years during the funding period. Among these individuals with small pulmonary nodules, we assume (based on data from KPSC) that 3.0% will be diagnosed with lung cancer, resulting in a sample size of approximately 1,056 patients with cancerous nodules.

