We will continue recruitment through the end of the study to collect additional data for HTE analyses with greater statistical power for Aim 1. We assume 10% loss to follow-up before final diagnosis is established based on KPSC membership data. This yields an estimated sample size for analyses of 960 individuals with cancerous nodules for Aim 1, and 32,000 individuals with small nodules for Aims 2-4.

Aim 1: For the primary outcome, the baseline risk of progression has not been reported. Conservatively, we assume that 5% of patients will progress from a tumor ≤ 15 mm to a tumor > 20 mm during the surveillance period. Assuming a two-sided alpha of 0.05, and an intraclass correlation coefficient (ICC) of 0.01, a sample size of 888 unique patients with cancerous lung nodules (444 per arm) is required to achieve 83% power to detect an absolute increase in tumor progression of 5 percentage points. Thus, our anticipated sample size of 960 unique patients with cancerous lung nodules provides adequate power to show non-inferiority of the less intensive surveillance strategy for our primary outcome of lung cancer stage $> T1a$ at diagnosis. The most uncertainty in our assumptions is for the ICC. We will have at least 80% power to detect a 5% increase in our primary outcome for ICC values of 0.012 or less. At the baseline ICC value of 0.01, a total sample size of 32,560 enrolled (including 888 patients with cancerous nodules) will have 0.83 power; for an ICC value of 0.012, a total sample size of 35,200 enrolled (960 patients with cancer) will also have 0.83 power.

Aim 2: Prior studies of anxiety and distress in lung cancer screening have shown that the identification of a lung nodule leads to anxiety and emotional distress that subsequently dissipates over 1-2 years.^{56 63 52} For our analyses of anxiety and emotional distress, we will have $> 90\%$ power to detect an effect size of 0.22 standard deviation, assuming an ICC of 0.01, even if the response rate is as low as 5%, resulting in an estimated sample size of approximately 792 respondents in each arm.

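### Both 83% power figures for Aim 1 assume a normal test and 24 equal sites; with t on about 22 df they fall to 80%, leaving no reserve at ICC 0.012

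*Combined protocol and SAP*

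**What the plan says.** The Aim 1 paragraph of *Sample size and power calculations by aim* sets out these inputs:

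- Error rate and clustering: "Assuming a two-sided alpha of 0.05, and an intraclass correlation coefficient (ICC) of 0.01".
- Baseline risk: "we assume that 5% of patients will progress from a tumor" of at most 15 mm to one above 20 mm.
- Required number: "a sample size of 888 unique patients with cancerous lung nodules (444 per arm"), which "is required to achieve 83% power to detect an absolute increase in tumor progression of 5 percentage points".
- Anticipated number: 960 cancers, which the plan says "provides adequate power to show non-inferiority of the less intensive surveillance strategy".
- ICC tolerance: "We will have at least 80% power to detect a 5% increase in our primary outcome for ICC values of 0.012 or less". A further sentence gives 0.83 power for 960 cancers at ICC 0.012.

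The opening of the same section counts "24 individual study sites for cluster randomization". The analysis plan for H1a specifies hierarchical logistic regression with random site effects. No section states the power formula, the reference distribution or degrees of freedom for the treatment test, or an allowance for unequal numbers of cancers per site.

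**The concern.** The treatment effect is estimated from differences between sites, so its precision depends on 24 units and not only on several hundred patients. A normal reference treats the between-site variance as known. With 24 sites it is estimated, and the critical value rises from 1.960 to about 2.074. The equal-site design effect also understates the variance when sites contribute different numbers of cancers.

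The plan names the ICC as its most uncertain assumption and offers 0.012 as the value it can tolerate. If that tolerance has no reserve under a suitable test, a reader of an inconclusive non-inferiority result would be misled about how well the trial was powered.

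**Working it through.** **Inputs.** From the Aim 1 paragraph: one-sided 0.025 (two-sided 0.05), risk 5% in both arms, margin 5 points, 888 or 960 cancers, ICC 0.01 or 0.012. From the opening of the section: 24 sites. Assumption: 12 sites per arm.

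**Formula.** With m = N/24, the design effect is DE = 1 + (m − 1)·ICC and the effective number per arm is n = (N/2)/DE. The standardised margin is d = 0.05/√(2 × 0.05 × 0.95/n). Normal power is Φ(d − 1.960).

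**Step 1: reproduce the plan.**
- 888, ICC 0.01: m = 37, DE = 1.36, n = 444/1.36 = 326.5, d = 2.931, power = Φ(0.971) = 83.4%.
- 960, ICC 0.012: m = 40, DE = 1.468, n = 480/1.468 = 327.0, d = 2.933, power = 83.5%.

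Both match the plan. Reading the target as superiority (10% against 5%) gives about 68% for 888 cancers at ICC 0.01, so the figures are non-inferiority calculations with a normal reference and equal, or very nearly equal, sites.

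**Step 2: t reference, equal sites.** Replace the normal by a noncentral t with 24 − 2 = 22 df, noncentrality d and critical value 2.074.

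**Step 3: unequal sites.** Use DE = 1 + [(1 + CV²)m − 1]·ICC. The CV values are assumptions.

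| Cancers, ICC | Normal, equal | t22, equal | t22, CV 0.4 | t22, CV 0.6 | t22, CV 0.8 |
|---|---|---|---|---|---|
| 888, 0.01 | 83.4% | 80.0% | 78.3% | 76.2% | 73.4% |
| 960, 0.01 | 85.4% | 82.1% | 80.4% | 78.3% | 75.4% |
| 960, 0.012 | 83.5% | 80.05% | 78.0% | 75.5% | 72.2% |

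**Step 4: where the floor gives way.** With 960 cancers and t22, power is 80% when DE is about 1.470. With equal sites the limit is ICC = 0.470/39 = 0.01205, against 0.0156 with a normal reference. At ICC 0.012 under t22 the floor is lost once CV exceeds about 0.06. The same DE gives ICC limits of 0.470/45.4 = 0.0104 at CV 0.4, 0.470/53.4 = 0.0088 at CV 0.6 and 0.470/64.6 = 0.0073 at CV 0.8.

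**Step 5: what the documents imply about CV.**
- The Aim 3 outcomes text expects about 22,000 nodule patients at California sites. Table 1 and the randomisation section put 14 clusters there (11 KPSC areas and three universities). Taking these patients as part of the 35,200, the averages are 22,000/14 = 1,571 in California and 13,200/10 = 1,320 elsewhere, around a mean of 1,467. The SD between clusters is about 124, so CV is at least about 0.085 even if clusters within each group are identical.
- With 40 cancers per site on average and 3% risk, chance alone gives a CV of about √(0.97/40) = 0.156.
- Combined, √(0.085² + 0.156²) ≈ 0.18. For 960 at 0.012 this gives DE = 1.484, n = 323.5 and t22 power of about 79.6%.

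The sites were also chosen for diversity in size, and randomisation balances on CT volume, so the true CV is probably larger. Its value is not given.

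**Step 6: does the reference matter in practice?** A beta-binomial simulation (8,000 runs, 960 cancers, ICC 0.012, equal sites, true difference at the margin) rejected in 3.5% of runs with a normal reference and 2.8% with t22, against a nominal 2.5%.

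**The case against.** The printed arithmetic is not wrong under its own assumptions, and a normal approximation is common in planning. Four counter-arguments have force.

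- A reader might infer that the 80% floor holds only for a normal test on equal sites. The figures do not support that. It holds, barely, under t22 with equal sites (80.05%), and under a normal reference it survives unequal sites up to CV about 0.54. It fails when t and unequal sites are combined. The t22 limit of 0.01205 is so close to the stated 0.012 that the sentence may already come from a t calculation, although no section says so.
- A reader might also infer that the design delivers 72 to 78%. That is not a property of the documents. It needs an assumed CV of 0.4 to 0.8, and it describes 960 cancers at ICC 0.012. The anticipated 960 cancers at the baseline ICC of 0.01 keep 82.1% under t22 with equal sites, and at least 80% up to CV about 0.45.
- The design effect in step 3 is conservative for a random-effects model. Multiplying n from the equal-site formula by 1 − CV²·λ(1 − λ), with λ = m·ICC/(m·ICC + 1 − ICC), gives 78.6%, 76.7% and 73.9% for 960 at 0.012 (CV 0.4, 0.6, 0.8). Simulation with size-weighted analysis gave about 79% at CV 0.4 and 76% at CV 0.8.
- Small inequality costs little: CV 0.18 takes the critical case only to about 79.6%.

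All four stand, and they narrow the point. They do not rescue the two 83% figures, which fall by more than 3 points under t22 before any inequality is considered.

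**Conclusion.** The two 83% figures rest on a normal reference and equal sites, neither stated. With t on about 22 df they become 80.0% and 80.05%. The anticipated case that the plan does not print, 960 cancers at ICC 0.01, is 82.1%. The ICC tolerance of 0.012 has no reserve: under t22 it is lost at any CV above about 0.06, and the documents' own figures imply more than that. How far power falls beyond this depends on an unstated CV. Over an assumed 0.4 to 0.8 it is about 78 to 72% (960, ICC 0.012), 78 to 73% (888, ICC 0.01) and 80 to 75% (960, ICC 0.01), and up to about 1.6 points higher with the mixed-model formula.

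This rests on 12 sites per arm and 22 df. The H1a models adjusted for facility-level factors could leave fewer df, which is not counted here. The documents do not support saying that the trial is known to have less than 80% power. The supported conclusion is that the stated power is too favourable and its basis is not disclosed.

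**What to change.** In the Aim 1 power paragraph:

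1. State the method: a non-inferiority comparison of two proportions, one-sided 0.025, t reference with about 22 df, and the number of sites per arm.
2. Use a design effect that allows for the expected variation in cancers per site. Give the CV as an assumption and show a range, for example 0 to 0.8.
3. Replace both 83% figures with the resulting values, and add the anticipated case of 960 cancers at ICC 0.01.
4. Qualify or lower the ICC limit in the sentence promising at least 80% power. Either say that 0.012 applies only to equal sites, or give the limit for each assumed CV.

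In the H1a analysis section, name the reference distribution and df for the treatment effect so that test and power statement agree.

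The cost is text only. Design, sample size and data collection are unchanged. The stated power becomes less favourable, and below 80% over part of the plausible range.

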Data Collection and Patient Enrollment: Participants will be enrolled passively and added to the study cohort by the interpreting radiologist who identifies a pulmonary nodule. This will facilitate enrollment of all eligible patients. All adult patients undergoing chest CT who are identified as having a nodule ≤ 15 mm, not previously identified, are potentially eligible. The radiologist will interpret the CT scan based on radiographic and clinical information as per usual clinical practice and determine if the patient meets study criteria. If so, the radiologist will include pre-specified language provided by our trial into the standard dictated radiologist's report. This language will trigger a series of automated steps, to be executed in a site-specific manner according to local practices and workflow: a) inserting standardized text with the recommended protocol for surveillance in the dictated report; b) sending an IRB-approved notification letter to the patient; c) sending a notification to the provider who ordered the CT scan; and d) sending patient data to a local hospital-based study repository. Participants will not be compensated for use of their data or for completing survey questions in this study, although we will hold a raffle to encourage participation.

Each hospital will be provided with appropriately formatted templates for radiologists (often called “canned reports”) to insert into the dictated radiology transcripts. Templates will summarize findings (size and imaging characteristics of the nodule), and recommendations for surveillance based on the assigned protocol. Templates will not need to be used exactly as written and can be tailored by radiologists for each patient.

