H3a: Among all participants with a lung nodule ≤ 15 mm, more intensive surveillance will be associated with greater nodule-related resource utilization, including more frequent use of CT scanning, PET scanning and invasive biopsy.

H3b: Among all participants with a lung nodule ≤ 15 mm, more intensive surveillance will be associated with a greater number of serious complications related to invasive procedures, including pneumothorax, pneumothorax requiring tube thoracostomy, bleeding, acute respiratory failure, acute renal failure and acute myocardial infarction.

H3c: Among all participants with a lung nodule ≤ 15 mm, more intensive surveillance will be associated with greater total exposure to diagnostic radiation than less intensive surveillance.

H4: Among all participants with a lung nodule ≤ 15 mm, more intensive surveillance will be associated with worse adherence to the surveillance protocol than less intensive surveillance, when measured at the level of the interpreting radiologist, the ordering provider and the patient.

Analysis Plan

In most cases, the unit of analysis will be the individual patient. All primary analyses will be by intention to treat, although we will also perform sensitivity analyses by surveillance imaging actually received. The intention to treat population will include all patients with qualifying nodules, even ones who do not undergo surveillance as the initial step in their evaluation (i.e., patients that proceed directly to tissue diagnosis). Sensitivity analyses will evaluate outcomes by strategy recommended and by surveillance imaging received.

Descriptive statistics will be generated for continuous variables (e.g., mean, standard deviation, median, range) and categorical variables (frequency) at baseline and follow-ups when appropriate. Bivariate analyses will include comparisons of means or medians (as appropriate) for continuously measured variables, cross tabulations of categorical variables, and Kaplan-Meier plots for time to event outcomes. Count outcomes, such as the number of procedure-related complications, will be treated as Poisson random variables. Analysis of time to

diagnosis, treatment, and survival will use Cox regression, after checking the proportionality assumption by creating log-minus-log plots.

H1a - Primary endpoint –lung cancer stage >T1a at diagnosis:

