Aim 3: The primary outcome for this aim is the total number of non-invasive and invasive procedures performed from the date of the index CT scan to the end of surveillance. We assume that patients who undergo more intensive surveillance will have 3.5 procedures on average. A sample size of 32,000 individuals with small nodules provides 90% power to detect a difference of 0.14 standard deviations for this outcome, assuming a two-sided alpha of 0.05 and an ICC of 0.01.

We will also compare the frequency of invasive testing among individuals with benign nodules. Based on data from the NLST, we assume that 5% of patients with benign nodules will undergo at least one invasive test. With an estimated sample size of 15,520 individuals with benign nodules in each group, and assuming a 2-sided alpha level of 0.05 and an ICC of 0.01, we will have 90% power to detect a difference between groups in the use of invasive testing of 3.4 percentage points.

Aim 4: For the analysis of radiologist adherence to inclusion of the recommendation for surveillance per protocol in the radiology report, we assume that radiologists will adhere to the assigned protocol for at least 85% of participants in the more intensive group. We estimated the ICC to be 0.19 based on preliminary data on radiologist variability in number of enrolled patients at the KPSC facilities. Assuming a 2-sided alpha of 0.05, we need to review at least 130 reports for enrolled patients at each participating facility to achieve 80% power to detect an improvement in adherence of 5.0 percentage points.

For the analysis of ordering physician adherence with ordering the surveillance test according to the assigned protocol, we assume that 80% of physicians in the more intensive group will be adherent. Assuming a 2-sided alpha of 0.05, our sample size of 16,000 individuals with small nodules in each group will provide >90% power to detect an improvement in adherence of 5.3 percentage points, assuming an ICC of 0.01-0.19.

For the analysis of patient overall adherence with surveillance, we assume that 27% of participants in the more intensive group will be non-adherent, based on the results of our study of guideline-concordant follow-up in veterans with pulmonary nodules.²⁴ Assuming a 2-sided alpha of 0.05, our sample size of 16,000 individuals with small nodules in each group will provide 90% power to detect an improvement in non-adherence of 5.9 percentage points, assuming an ICC of 0.01.

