All subjects 35 years or older who have at least one newly identified pulmonary nodule measuring ≤15 mm detected on a chest CT conducted for any reason will be passively enrolled into the study. Exclusion criteria include subjects with a known extrathoracic cancer within the past 5 years. For sufficient power for establishing non-inferiority of the less intensive strategy, we estimate that we will need to identify 279,500 subjects who underwent chest CT to identify 35,200 subjects with small lung nodules of interest. Subjects with nodules will be identified by practicing radiologists, who will trigger an alert in the Radiology Information System (RIS) to embed a template with the recommended surveillance protocol into the dictated radiology report. In addition, sites will use manual and/or automated methods to search radiology reports and identify subjects with small nodules who may not have been enrolled, thereby allowing us to measure adherence at the level of the interpreting radiologist. Additional alerts flowing from the RIS to the Electronic Medical Record (EMR) will generate letters or emails to the ordering physician and patient notifying them of the results, explaining the results and the recommendation for follow-up, describing the study goals and duration, and specifying the types of data to be collected. Contact information for the project coordinator and Principal Investigator (PI) will be provided. An alert will also be created to send the radiology report to the local site data repository that will then be used by protocol coordinators to extract study outcome information through linkage with the internal health systems database and cancer registries. Patients will complete validated measures of anxiety, emotional distress and general health status via the Internet. Patient- and physician-level data will be exported to the central data repository at Data Coordinating Center.

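### The radiologist-adherence sample is drawn from enrolled patients, although the act that enrols a patient also inserts the recommendation being scored; the planned search for non-enrolled patients is not carried into H4

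*Combined protocol and SAP*

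**What the plan says.** **Enrolment.** Under Data Collection and Patient Enrollment, a radiologist who finds a qualifying nodule adds trial wording to the report. That wording sets off several automated steps, among them "inserting standardized text with the recommended protocol for surveillance in the dictated report" and transfer of the patient's data to the local study repository. Recruitment and Informed Consent repeats that enrolment happens when the radiologist triggers the alert. Radiologists may adapt the template to the patient.

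**Endpoint and hypothesis.** Radiologist adherence is the first-listed Aim 4 primary endpoint. H4 predicts worse adherence with more intensive surveillance among all participants, "when measured at the level of the interpreting radiologist, the ordering provider and the patient".

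**Sample.** The Aim 4 power paragraph says "we assume that radiologists will adhere to the assigned protocol for at least 85% of participants in the more intensive group" and "we need to review at least 130 reports for enrolled patients at each participating facility", in order "to achieve 80% power to detect an improvement in adherence of 5.0 percentage points".

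**A different frame.** Human Subjects Involvement, Characteristics, and Design says sites will also search radiology reports for patients with small nodules who may not have been enrolled, "thereby allowing us to measure adherence at the level of the interpreting radiologist".

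**Elsewhere.** Table 4 refers to all patients with nodules, with a random one-in-ten sample for detail. Aim 4 Outcomes refers to a sample of transcripts without naming the frame. Data Collection and Patient Enrollment sends a sample of all chest CT reports for quality improvement. The H4 analysis text builds adherence indicators for the ordering provider and the patient only.

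**The concern.** Selection into the sample depends on the behaviour being measured. A radiologist who reports an eligible nodule and does not use the trial wording produces no enrolled patient, so that report cannot be scored as a failure. What remains visible is departure from protocol within enrolled reports, for example edited or wrong text.

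Two consequences follow. The level of adherence will be too high whenever missed eligible reports carry the assigned recommendation less often than enrolled ones. The comparison between arms can also be wrong in size or direction if radiologists in one arm use the trigger less. This endpoint tells readers how faithfully each protocol was delivered, so an estimate conditional on enrolment could be misread as an estimate of delivery.

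**Working it through.** **1. The plan's figure of 130.** Inputs from the Aim 4 power paragraph are 85% v 90%, two-sided alpha 0.05, power 80% and ICC 0.19. The sample size section gives 24 sites; I assume 12 per arm.

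Without clustering, n per arm = [1.96·√(2·0.875·0.125) + 0.8416·√(0.85·0.15 + 0.90·0.10)]² / 0.05² = 686.

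The plan supplies 12 × 130 = 1,560 reports per arm, an implied design effect of 1,560/686 = 2.27.

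- With ICC 0.19 at facility level, the design effect is 1 + 129 × 0.19 = 25.5, the effective n is 1,560/25.5 = 61 per arm, and power is about 0.13. More reports per facility cannot help: effective n cannot exceed 12/0.19 = 63.
- With ICC 0.19 at radiologist level, 130 is matched if each radiologist contributes 1 + (2.27 − 1)/0.19 = 7.7 reports, or about 130/7.7 = 17 radiologists per facility.
- ICC 0.01 at facility level also matches (design effect 2.29, power 0.797).

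The plan states neither the level of clustering nor the reports per radiologist, so 130 cannot be derived from its stated inputs alone. The source of the ICC is also indirect: "We estimated the ICC to be 0.19 based on preliminary data on radiologist variability in number of enrolled patients at the KPSC facilities". That describes enrolment counts, not adherence. I keep the implied design effect of 2.27 below.

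**2. Bias in the level.** Let a be adherence among enrolled reports, u the share of eligible reports where the trigger was not used, and r the adherence among those missed reports. Over all eligible reports, adherence is (1 − u)a + u·r, so the enrolled-only figure is too high by u(a − r). The bias is zero if r = a and reaches u·a if r = 0. The documents give neither u nor r.

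**3. Bias in the contrast (illustration).** Take the planning values as enrolled-report adherence, assume r = 0, and assume values for u:

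| Missed, more v less intensive | More intensive | Less intensive | Difference (less − more) |
|---|---|---|---|
| enrolled reports only | 85% | 90% | +5.0 points |
| 20% v 10% | 0.80 × 85% = 68% | 0.90 × 90% = 81% | +13.0 points |
| 10% v 20% | 0.90 × 85% = 76.5% | 0.80 × 90% = 72% | −4.5 points |

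**4. Power on the wider denominator.** Assume equal u in both arms, r = 0, a 5.0-point difference still targeted, and design effect 2.27:

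| Missed in both arms | Adherence, more intensive | n per arm, unclustered | Reports per facility for 80% power | Power at 130 |
|---|---|---|---|---|
| 5% | 80.8% | 875 | 875 × 2.274/12 = 166 | 0.70 |
| 10% | 76.5% | 1,041 | 1,041 × 2.274/12 = 197 | 0.62 |
| 20% | 68.0% | 1,305 | 1,305 × 2.274/12 = 247 | 0.53 |

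**The case against.** The strongest reply is that the plan already foresees the problem. It intends to search for non-enrolled patients in order to measure radiologist adherence, so the plan as a whole does not exclude this kind of non-adherence. That stands. But the search has no stated denominator, sample size or variable, and the only sizing text points to enrolled patients.

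A reader might infer that enrolled reports will be adherent almost by construction and that both arms will sit near a ceiling. The documents do not support that. Templates can be tailored, a report is scored on whether the recommendation is present and follows the protocol, and the planning value is 85%. Nor do the documents give frequencies showing that omission of the trigger is the main form of failure.

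A reader might also take the gap between about 45,000 qualifying patients and 35,200 enrolled as evidence of non-use. The sample size section ties that allowance to site variation in prior cancer and in nodules seen on earlier scans, and 35,200 is a planned minimum. The gap does not measure trigger use.

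Two further points limit the remedy. Both protocols derive from published guidelines, so a conforming recommendation can be dictated without the trigger. Exclusion Criteria also leaves several eligibility decisions to the radiologist, so some non-use is legitimate. Finally, H4 is framed among participants, which fits an enrolled-only sample, but that answers a narrower question than the one the search is said to address.

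**Conclusion.** The point holds as an inconsistency with a predictable bias. If the power paragraph is followed as written, a listed Aim 4 primary endpoint is estimated conditional on the act being scored. The level is then too high by u(a − r), provided missed reports adhere less often than enrolled ones. The arm contrast is distorted if trigger use differs by arm. The size is unknown because neither u nor r is given; the shifts from +5.0 to +13.0 or −4.5 points rest on assumed missed shares and on missed reports carrying no recommendation.

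H4 at radiologist level also has no defined analysis variable. This should be fixed, but it concerns one level of one Aim 4 endpoint. The Aim 1 primary analysis and its sample size are not affected.

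**What to change.** - **One denominator.** In Table 4, Aim 4 Outcomes, H4 and its analysis text, the Aim 4 power paragraph and the Human Subjects section, define the frame as all reports with an eligible nodule found by the planned search, whether or not the trigger was used.
- **Scoring.** Score each report on whether the assigned recommendation is present and per protocol, not on template use. Apply the Exclusion Criteria first, and do not count documented radiologist-judgement exclusions as failures.
- **Separate figure.** Report the enrolled-only result alongside, labelled as conditional on enrolment. If reports have already been drawn from enrolled patients only, that label is the minimum correction.
- **Analysis.** Add a radiologist-level adherence variable and a hierarchical model for H4, and state the level to which the ICC of 0.19 applies.
- **Feedback.** Show reports from before and after the early adherence feedback separately, since the PRECIS list says results are fed back early and poor adherence acted upon.
- **Power.** Restate the power or the detectable difference at 130 reports per facility, or increase the number.

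**Cost.** The search is already planned. Reported adherence will be lower, and eligibility of missed reports has to be checked, probably at the sites, because the sample of all chest CT reports is de-identified. Under the assumptions above, with 10% missed in both arms, power at 130 is about 0.62, and keeping 80% takes about 197 reports per facility.
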